Title: A Pull to be Close: the Differentiating Effects of Oxytocin and Grief Stimulus Type on Approach Behavior in Complicated Grief

NCT #: NCT04505904 Date: October 23, 2021

Objectives:

Our first aim was to identify whether bereaved individuals would show different motivational responses depending on whether stimuli represented their deceased spouse, or were general reminders of the loss (“non-specific grief”). We hypothesized that participants overall would show an approach bias for stimuli depicting their spouse, but would not show an approach bias for “non-specific grief” stimuli. Our second aim was to investigate whether response bias differed between CG and non-CG participants. Specifically, we hypothesized that participants with CG would exhibit a greater approach bias for spouse stimuli, compared to non-CG participants. Our third aim proposed differential effects of intranasal oxytocin in CG and non-CG participants (i.e., a group x condition interaction), where oxytocin would specifically increase relative approach bias for the spouse in CG only. This is based on prior work supporting individual differences in socio-emotional functioning as likely moderators of oxytocin effects (Bartz et al., 2011; Seeley et al., 2018).

Study Protocol

Participants gave written informed consent and were compensated \$200. Prior to their first session, participants provided three photos of their spouse, and three photos of a living loved one (identified via the WHOTO scale; Fraley & Davis, 1997). They completed self-report measures (e.g., demographics, health, length of relationship, time since the death), the Beck Depression Inventory-II (BDI-II; Beck et al., 1996), and Inventory of Complicated Grief (ICG; Prigerson et al., 1995). The ICG is a 19-item measure of complicated grief symptoms distinct from depression or anxiety and predictive of functional impairment, and showed high internal consistency in our sample ($\alpha = .92$).

Enrolled participants were categorized in the complicated grief (CG; n=17) or non- complicated grief (non-CG; n=22) group based on a clinical cutoff score of ≥ 25 on the ICG. A non-bereaved control group was not included in the current study because there was no available analogous stimulus to the deceased spouse for non-bereaved participants. Stratified sampling achieved representation of a full range of ICG scores ($M = 23.38$, $SD = 12.63$, range = 4-51).

Participants attended two experimental sessions 7-10 days apart. At each session, participants received a 24 IU dose of synthetic oxytocin (Syntocinon, Novartis, Switzerland) or placebo (all non-active ingredients of Syntocinon; Novartis, Switzerland) delivered via self- administered nasal spray. Participants and investigators were blind to condition until data analyses were complete. Order of oxytocin or placebo spray was randomized and counterbalanced across participants. After a 30-minute oxytocin rise-time, participants completed the AAT. They completed state measures before and after the task, and were debriefed after their second visit.

Task Description

Participants viewed three photos in each stimulus category: (1) deceased spouse, (2) living loved one, (3) stranger, (4) non-specific grief-related scenes such as a tombstone, casket, or hospital room, and (5) neutral scenes such as an outdoor picnic table or living room. Photos of a stranger were sex-matched to the spouse (for the living and deceased stimuli). Neutral environments (for the non-specific grief photos) were used to control for differences in person versus scene processing. Based on previous AAT designs (Derntl et al., 2011), photos were framed by a blue or yellow border. Participants were instructed to push or pull the joystick based on the frame color, not the photo's content. They completed the task twice per session, with reversed instructions on the second run (i.e., “*pull for yellow*” became “*push for yellow*”). Each seven-minute run of the task consisted of 144 2500ms trials (288 trials per visit, 576 trials total across runs/sessions; 500ms ITI). Order of instructions was randomized and counterbalanced across participants. Stimuli were presented via Inquisit 4 (2014), in a pseudorandomized order determined by genetic algorithm (Wager & Nichols, 2003).

Relative approach/avoidance bias was computed by subtracting median response time (RT; latency to joystick full extension) on PULL/approach trials in each stimulus category from PUSH/avoid trials in the same category (Rinck & Becker, 2007). Positive response bias values indicate relative approach bias; negative values indicate relative avoidance bias.

Statistical Analysis

Trials with RTs \leq 1st percentile (placebo: 463ms, oxytocin: 473ms) or \geq 99th percentile (placebo: 1717ms, oxytocin: 1711ms) were discarded as per previous AAT studies (Rinck & Becker, 2007). After discarding outliers and missed trials, none had $>10\%$ missing data except

for one participant (14% in the placebo condition). Data cleaning, visualization, and analysis were completed with R 3.6.3 using ‘`dplyr`’, ‘`ggplot2`’, ‘`afex`’, ‘`emmeans`’, ‘`nlme`’, and ‘`psych`’ packages (Lenth, n.d.; Pinheiro J, Bates D, DebRoy S, Sarkar D, R Core Team (2019), n.d.; Revelle, n.d.; Singmann, Bolker, Westfall and Aust, n.d.; Wickham, H., François, R., Henry, L., and Müller, K., n.d.).

Statistical analyses included repeated measures ANOVAs with tests of *a priori* contrasts on the estimated marginal means to predict bias scores. In addition, we repeated each analysis using mixed effects linear modeling. Mixed effects models yield higher power due to the larger number of observations at the trial level (288 observations per participant, per session) compared to the bias scores, which are computed from median RTs averaged across trials (five observations per participant, per session). The mixed effects linear models used individual PUSH/PULL trial RTs as the outcome rather than bias scores, and included joystick response direction (PUSH or PULL) as an additional fixed effect. Results did not change substantively using the mixed effects models, and are more difficult to interpret because of the added predictor. Further, an RT in one direction alone (rather than relative to the other direction) is a less direct index of response bias than bias scores, and thus, bias scores are easier to interpret. Therefore, we present the ANOVA results for ease of interpretation, and only report the mixed effects models when needed to demonstrate results requiring more power.

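### The Aim 3 group-by-condition test is exposed to session change: balance of spray order within CG and non-CG is not reported, and no session or order term is named

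*Combined protocol and SAP*

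**What the plan says.** The third aim (Objectives) proposes "differential effects of intranasal oxytocin in CG and non-CG participants (i.e., a group x condition interaction", with oxytocin expected to raise approach bias for the spouse in CG alone. Under Study Protocol, "Enrolled participants were categorized in the complicated grief (CG; n=17) or non- complicated grief (non-CG; n=22) group"; the dividing line is an ICG score of 25 or more.

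The design is a two-period crossover: "Participants attended two experimental sessions 7-10 days apart", with oxytocin at one session and placebo at the other. The only statement on allocation of the sprays is "Order of oxytocin or placebo spray was randomized and counterbalanced across participants". No stratification factor is named, and no counts of order by group are given.

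On timing, Study Protocol states "Prior to their first session, participants provided three photos of their spouse"; the ICG appears in the next sentence, among the self-report measures. It adds that "Stratified sampling achieved representation of a full range of ICG scores", which concerns recruitment, not the assignment of spray order.

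Statistical Analysis describes repeated measures ANOVAs on bias scores and a parallel trial-level mixed model. The only extra fixed effect named for the mixed model is joystick direction. Session and order are named in neither.

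**The concern.** In a two-period crossover, each person's oxytocin minus placebo difference contains the session 1 to 2 change, with a sign that depends on which spray came first. For the average oxytocin effect, overall balance of order cancels that change. Aim 3 contrasts the effect between two groups, so the change cancels only if order is balanced in each group or is handled in the model. The documents give no assurance of either.

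A change in bias between sessions is plausible, because participants do the same task 7-10 days apart and the photo set appears to be reused. It could also differ between CG and non-CG, for example if they habituate to spouse photos at different rates. What is at stake is whether an observed group difference in the oxytocin effect, or its absence, partly reflects which spray came second in each group.

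**Working it through.** **Inputs from the documents.** 17 CG and 22 non-CG, 39 in all (Study Protocol); two sessions, one spray each (Study Protocol); outcome is PUSH minus PULL median RT (Task Description). The plan states no order-by-group figure, power calculation or significance level, so there is no figure of its own to reproduce.

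**Assumptions.** Order split 20:19 or 19:20 overall and otherwise random with respect to group; no carryover; two-sided 5% level; session change of 0.25 to 1.0 SD, in units of the within-sequence SD of the oxytocin minus placebo difference.

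**Step 1: the shift.** For group g, let τ_g be the oxytocin effect on bias, π_g the session 2 minus session 1 change in bias, and p_g the share given oxytocin first. Then

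mean difference in group g = τ_g + π_g(1 − 2p_g).

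The unadjusted Aim 3 contrast is therefore off by π_CG(1 − 2p_CG) − π_non(1 − 2p_non). If the change is the same in both groups, this is −2π(p_CG − p_non).

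**Step 2: chance imbalance.** With 20 of 39 given oxytocin first, the number X in CG is hypergeometric, with variance 17 × (20/39) × (19/39) × (22/38) = 2.459 and SD 1.568. Since p_CG − p_non = X(1/17 + 1/22) − 20/22, its SD is 1.568 × 0.1043 = 0.164. The multiplier of π has SD 2 × 0.164 = 0.327, and its absolute value is 0.5 or more in 11.1% of randomisations. The CG split is 11:6 or worse in either direction in 20.0%, and 12:5 or worse in 5.4%.

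**Step 3: effect on the test.** Simulated type I error for given splits (20,000 runs each, common session change, no order term):

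| CG oxytocin-first | non-CG oxytocin-first | p_CG − p_non | Shift | Type I error at π = 0.25, 0.5, 1.0 SD |
|---|---|---|---|---|
| 9/17 | 11/22 | 0.029 | −0.06π | 4.3%, 2.8%, 0.7% |
| 11/17 | 9/22 | 0.238 | −0.48π | 5.6%, 7.3%, 9.5% |
| 12/17 | 8/22 | 0.342 | −0.68π | 7.2%, 13.1%, 25.7% |

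Averaged over all randomisations the error stays at 5.0-5.1% for these values of π. The SD of the contrast rises from 0.32 (π = 0) to 0.36 (π = 0.5) and 0.46 (π = 1.0). For an assumed true group difference of 0.9 SD and π = 0.5, power is 68% without an order term and 76% with one.

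The first row shows that balance alone is not enough. If session is left out of the model, its variance stays in the error term and the test becomes conservative.

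**Step 4: what a model term does.** With a common order term, simulated type I error is 4.6-5.3% in every scenario run. If the session change occurs in CG only, an 11:6 split shifts the unadjusted contrast by 5/17 = 0.29 of that change; a common order term leaves 0.05-0.09 of it (0.08-0.13 at 12:5). The unweighted mean of the two order cells gives the session change weight +½ and −½ within each group, so nothing is left.

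**Step 5: cost in precision.** The variance of an order-balanced group mean is ¼(1/a + 1/b) for cells a and b, against 1/n unadjusted. The unadjusted sum is 1/17 + 1/22 = 0.1043.

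- CG 11:6 with non-CG 9:13: 0.0644 + 0.0470 = 0.1114; √(0.1114/0.1043) = 1.03. With non-CG 8:14 the ratio is 1.04.
- CG 12:5 with non-CG 8:14: 0.0708 + 0.0491 = 0.1199; ratio 1.07. With non-CG 7:15 it is 1.09.

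**The case against.** Several stronger readings are tempting, and the documents do not support them.

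- A reader might infer that order was balanced over the whole sample instead of within groups. The wording would also fit separate lists for each ICG stratum. What can be said is that within-group balance is not reported.
- A reader might infer that group membership was certainly known when order was assigned. This is likely, but the phrase about timing governs the sentence on photos, and the date of categorisation is not stated.
- A reader might infer that the Aim 3 test is biased. It is not, over randomisations; inflation is conditional on an unlucky realised split.
- A reader might infer that an imbalance would produce the predicted CG-only pattern. A fixed overall split means that an 11:6 split in CG forces 9:13 or 8:14 the other way in non-CG, so a common session change moves both groups (by 0.29 of the change in CG and 0.18 or 0.27, in the opposite direction, in non-CG). If bias falls at session 2 and oxytocin comes second more often in CG, the predicted effect is masked, not mimicked.

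The mechanism is also narrower than general practice. Faster responding that is common to PUSH and PULL cancels in the bias score, and a change equal across stimuli cancels in a contrast of spouse with another category. Only a change in relative bias matters, and nothing in the documents says how large it is.

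These points limit the claim, but none removes the gap. The trial has one realised allocation, its order counts by group are not shown, and no named model term would protect the contrast if they are unequal.

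**Conclusion.** The point holds as a gap in analysis and reporting, not as a demonstrated flaw in the randomisation. If order was balanced only overall, a CG split of 11:6 or worse has a 20% chance and 12:5 or worse about 5%. The Aim 3 contrast would then move by roughly half to two-thirds of any common session change in bias (0.48 and 0.68 in the examples worked). The direction is unknown, so an apparent effect may be inflated or hidden. On average the cost is precision.

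The conclusion rests on an assumed 19:20 overall split, no carryover and a non-zero session change in the bias score. If the sponsor shows near-equal order within each group, the shift is at most about 0.06 of a common change. The case for modelling session then rests on precision. It merits a change because the remedy uses data already in hand.

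**What to change.** 1. State whether spray order was assigned within ICG groups, and tabulate order by CG and non-CG.
2. Add order and order x group to the Aim 3 analysis of the oxytocin minus placebo difference. In the repeated measures ANOVA these are order x condition and order x group x condition. Read the group contrast at equal weight for the two orders, which is the same as taking the unweighted mean of each group's two order cells. A common or group-specific session change then cancels.
3. Where the trial-level mixed model is reported, let the matching session terms interact with joystick direction, since bias is the direction contrast.

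The cost is one table and one re-run, with standard errors about 3-4% wider at an 11:6 CG split and 7-9% wider at 12:5, before any gain from removing session variance. Assigning order in blocks within ICG strata cannot help the 39 already enrolled; it applies only to further enrolment or a future study, where it would cost two lists in place of one.

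### Does crediting the mixed models' power to trial count, with no random effects stated, undermine the results they support?

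*Combined protocol and SAP*

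**What the plan says.** The Statistical Analysis section describes repeated measures ANOVAs on bias scores, each repeated as a linear mixed model on single-trial response times. The reason given for the second analysis is that "Mixed effects models yield higher power due to the larger number of observations at the trial level". It sets "288 observations per participant, per session" against "five observations per participant, per session". The mixed models "included joystick response direction (PUSH or PULL) as an additional fixed effect". No random intercept, random slope, covariance structure or degrees-of-freedom method is named.

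The section then reports agreement: "Results did not change substantively using the mixed effects models". On that basis "we present the ANOVA results for ease of interpretation", and the authors "only report the mixed effects models when needed to demonstrate results requiring more power".

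The Task Description gives the trial count ("Each seven-minute run of the task consisted of 144 2500ms trials", two runs per session). It defines each bias score as the median PUSH time minus the median PULL time within a stimulus category.

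**The concern.** Two things look wrong.

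- **The power rationale.** Aims 2 and 3 (Objectives) compare complicated-grief with non-complicated-grief participants, 17 against 22 (Study Protocol). Splitting each person's data into more rows adds no people. A claim that power comes from row count suggests the rows may have been treated as independent.
- **The error term.** A random intercept cancels in PUSH minus PULL, so it does not protect a test of bias. If true bias differs between people and the model has no by-participant slope for direction, its standard errors are too small.

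The plan reserves these models for results needing more power, which may be results that the ANOVA does not support. If such a result came from a model without slopes, its p-value could not be trusted.

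**Working it through.** **1. The plan's counts.** 144 × 2 = 288 trials per session and 288 × 2 = 576 per participant, as stated. Five categories give five bias scores per session. Over 17 + 22 = 39 participants this is 39 × 576 = 22,464 trial rows before discards, against 39 × 10 = 390 bias scores, from the same trials.

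**2. Assumptions.** The documents give neither the trial-to-trial SD (s) nor the between-person SD of true bias.
- The placebo trimming limits bound s at about (1717 − 463)/(2 × 2.326) = 270 ms if times are normal; 150 to 250 ms is used below.
- Trials per category, direction and session: m = 288/10 = 28.8, assuming an equal split over categories.
- Slope SD: 50 ms as an illustration, with smaller values also shown.

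**3. Does row count itself add power?** Restricted maximum likelihood models were fitted to simulated spouse trials (39 people, slope SD 50 ms). The table gives standard errors in ms.

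| | Slope model | Participant-level mean bias | Intercept only |
|---|---|---|---|
| Aim 2, s = 150 | 18.4 | 18.4 | 9.5 |
| Aim 2, s = 250 | 22.2 | 22.2 | 15.6 |
| Aim 3, s = 150 | 24.4 | 24.3 | 19.0 |
| Aim 3, s = 250 | 35.4 | 34.5 | 31.1 |

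A model with slopes is no more precise than one mean bias per person, so row count is not the source of power.

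**4. Is the higher-power claim therefore false?** The plan compares the mixed models with scores built from medians, not means. Simulated power (s = 200 ms, group difference 40 ms, 58 trials per direction over both sessions) was as follows. In balanced data the slope model is equivalent to a t test on mean bias, and it was computed that way.

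| Slope SD | Slope model | Median bias scores |
|---|---|---|
| 20 ms | 82% | 68% |
| 40 ms | 60% | 50% |

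A repeat of the mean-against-median comparison gave 82% v 68% and 61% v 52%, and the advantage held with skewed response times. The claim is right; only its explanation is wrong.

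**5. Do trials matter at all?** For Aim 3, the trial-noise variance of a person's oxytocin-minus-placebo change in bias is 4s²/m. This is 4 × 150²/28.8 = 3,125 ms², or 4 × 250²/28.8 = 8,681 ms². At a change SD of 50 ms the between-person part is 2,500 ms². Trial noise is then 3,125/5,625 = 56% to 8,681/11,181 = 78% of the total. Precision depends on both trials and people.

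**6. What if slopes were omitted?** Type I error = 2 × (1 − Φ(1.96/√(1 + SD²/v))), with v = s²/m for Aim 2 (two sessions averaged) and 4s²/m for Aim 3.
- Aim 2, SD 50 ms: v = 781 (s = 150) gives 33.9%; v = 2,170 (s = 250) gives 18.2%.
- Aim 3, SD 50 ms: v = 3,125 gives 14.4%; v = 8,681 gives 8.4%.
- SD 20 ms, s = 200: 8.4% for Aim 2 and 5.8% for Aim 3.
- SD 0: 5%. Aim 3 also stays at 5% if each person's bias is stable between sessions.
- The rate passes 10% when the SD exceeds 0.648√v: 18–30 ms for Aim 2, 36–60 ms for Aim 3.

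Fitted models with slopes and 37 degrees of freedom held 2.0–5.9%. Using a normal in place of a t reference with 37 degrees of freedom costs little: 5.8% against 5.0%.

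**The case for a change.** The best argument for a change is that the reserved models are used exactly where an omitted slope would do most harm. Agreement between the two analyses in general cannot vouch for a result shown only by the mixed model. The third aim itself supposes that people differ in their response to oxytocin, so zero variation is not an obvious default. Stating the model would cost one sentence.

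Part of this stands. The row-count explanation is wrong, the inflation under omitted slopes is real arithmetic, and anyone reporting such a model should state its random effects.

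It does not amount to a fault in the plan. Silence about random effects is not evidence of an intercept-only fit. The document has no results section, so it would not be expected to list results that rest on a mixed model alone; there may be none. The size depends on a between-person SD that the documents do not give.

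Rewording would gain little. Saying only that 39 participants limit precision would be as incomplete as the present sentence, given the 56–78% share of trial noise in step 5. Prescribing a full slope structure is not free either: the fully correlated version was singular in 7–44% of simulated fits at slope SD 50 ms, and in 93% at SD 0 (s = 150).

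**Conclusion.** No change to the plan is needed. Its statement that the mixed models have more power than the median-based ANOVA is supported, by about 10 to 14 percentage points in the simulated cases, although the reason it gives is mistaken. Correcting that reason would alter no analysis and no result.

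The unstated random effects are a gap in detail that an analyst would ordinarily fill by including the slope for the tested contrast and stating it with any mixed-model result. The error rates of 18–34% and 8–14% are conditional on omitted slopes and on an assumed slope SD of 50 ms; they are not estimates for this trial. Harm would also require a conclusion resting on a mixed model alone. The presented ANOVA works on participant-level scores, so it is unaffected whichever structure was fitted.

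### The mixed model is shown only where extra power is judged necessary, with no criterion and both result sets already known, so any aim could get an unadjusted second test

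*Combined protocol and SAP*

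**What the plan says.** The Objectives section sets three aims: spouse versus non-specific grief stimuli, complicated grief (CG) versus non-CG participants, and a group-by-condition interaction for oxytocin.

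Under Statistical Analysis, the first method is a repeated measures ANOVA on median-based bias scores with planned contrasts. The section then says "we repeated each analysis using mixed effects linear modeling", this time on individual trial response times with joystick direction as an extra fixed effect. It credits the mixed model with more power because it uses 288 trials per participant per session, against five bias scores.

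The two are then compared in the past tense: "Results did not change substantively using the mixed effects models". A response time in one direction alone "is a less direct index of response bias than bias scores". The section concludes: "Therefore, we present the ANOVA results for ease of interpretation", and the authors "only report the mixed effects models when needed to demonstrate results requiring more power".

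The document does not say what makes a mixed model necessary, which contrasts call for more power, what alpha applies, or what random effects were fitted.

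**The concern.** The reporting rule can be read in two ways. On the first, certain effects, such as the group-by-condition interaction, were recognised from the design as needing more power, and the mixed model was meant for those. On the second, the mixed model is brought in when the ANOVA contrast is not significant. That is selection in one direction, because a non-significant mixed model would never displace a significant ANOVA. The text names no contrast in advance, so it does not exclude the second reading.

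The rule also fits poorly with the statement that the two analyses agreed. A result that needs the mixed model in order to be demonstrated is one where the two analyses may fall on opposite sides of the significance threshold.

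Two things are at stake. If the second reading was followed, each aim had a second, unadjusted chance of a positive finding. On either reading, someone given only the ANOVA results cannot see, contrast by contrast, where the mixed model agreed, disagreed or was left out.

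**Working it through.** **Inputs from the document.** 17 CG + 22 non-CG = 39 participants and two sessions (Study Protocol). Two runs of 144 trials per session and five stimulus categories (Task Description). Trimming limits of 463 and 1717 ms for placebo, 473 and 1711 ms for oxytocin (Statistical Analysis).

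**The plan's own figure.** 2 × 144 = 288 trials per session and 2 × 288 = 576 in total, as stated. Before exclusions the mixed model has 39 × 576 = 22,464 rows and the ANOVA has 39 × 2 × 5 = 390 bias scores. Both rest on the same 39 people.

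**Step 1. Two correlated tests.** Assume each analysis is a valid two-sided 5% test and that a finding is claimed if either is significant. With correlation ρ between the test statistics, the per-aim error is p = 1 − P(|Z₁| < 1.96 and |Z₂| < 1.96). Over three aims treated as independent it is 1 − (1 − p)³.

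| ρ | per aim | three aims |
|---|---|---|
| 0 | 0.0975 | 0.265 |
| 0.5 | 0.091 | 0.248 |
| 0.7 | 0.0835 | 0.230 |
| 0.8 | 0.078 | 0.216 |
| 0.9 | 0.070 | 0.197 |
| 0.95 | 0.065 | 0.182 |
| 1 (one test) | 0.05 | 0.143 |

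The document does not give ρ. Both analyses use the same trials, so it should be high.

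**Step 2. Simulation under no effect.** There were eight settings with 5,000 replicates each. Assumptions:
- 29 trials per category, direction and session (288/5/2 = 28.8, assuming equal allocation).
- Gamma trial noise with SD 220 ms and shape 2 or 4. As a plausibility check, the trimming limits imply a total SD of (1717 − 463)/4.653 = 270 ms and (1711 − 473)/4.653 = 266 ms under a normal approximation. A within-participant SD of 220 ms is compatible with this but remains an assumption.
- Between-participant SD of true bias 0, 30, 60 or 100 ms, with half the variance stable and half session-specific.
- ANOVA contrast: t-test on median-based bias. Mixed model: participant-level t-test on means, which is equivalent to by-participant slopes in balanced data.
- Aim 1 is spouse minus grief bias, Aim 2 the group difference in spouse bias, and Aim 3 group by condition on spouse bias.

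| | either significant | mixed model only | either, mixed model at critical value 1.96 |
|---|---|---|---|
| Aim 1 | 6.3–8.1% | 1.4–2.7% | 6.7–8.6% |
| Aim 2 | 6.5–8.4% | 1.4–3.5% | 7.1–9.0% |
| Aim 3 | 7.3–8.3% | 2.0–3.3% | 7.8–8.8% |

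The ANOVA contrast alone was significant in 4.4–5.7% of replicates, so the second look adds 1.4–3.5 percentage points. The Monte Carlo standard error is about √(0.07 × 0.93/5000) = 0.0036, or 0.4 points. In a repeat with 1,000 replicates per setting the two statistics correlated 0.70–0.95. Step 1 gives 8.35% to 6.5% over that range, which agrees with the simulation.

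**Step 3. If the mixed model has only a random intercept.** Take an Aim 2 comparison with an assumed trial SD of 200 ms, 58 spouse trials per direction over two sessions, and between-participant SD of bias τ. The true variance of a participant's bias is τ² + 2 × 200²/58 = τ² + 1379. The model assumes about 2 × (200² + τ²/4)/58. The rejection rate under no effect is 2 × [1 − Φ(1.96 × √(assumed/true))].
- τ = 20: √(1383/1779) = 0.882, giving 8.4%.
- τ = 40: √(1393/2979) = 0.684, giving 18.0%.
- τ = 60: √(1410/4979) = 0.532, giving 29.7%.

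A simulation of 4,000 runs gave 8%, 18% and 29% for these, and 6% at τ = 0. The participant-level test stayed near 5% throughout.

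**The case against.** The strongest reply is that no selective use has been shown. The ANOVA is the stated default, reasons are given, and any mixed model relied on would be reported as one, so a switch would be visible. That is correct. The firm part of this point is the missing criterion; the inflation is conditional on the second reading. If no aim switched, the reported p-values are simply those of the ANOVA.

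Similar estimates with a smaller standard error in one model would also fit both the agreement statement and the reporting rule. This is fair, and is why the two sentences can only be said to sit uneasily together. The agreement statement is still a blanket one, with no figures for any contrast.

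The simulation has limits. It stands in for the mixed model with participant-level means, so its inflation comes from means and medians disagreeing rather than from trial-level power. It tests spouse minus grief for Aim 1, assumes equal trial allocation although 144/5 is not a whole number, and counts effects in either direction although the hypotheses for Aims 2 and 3 are directional. Counting only the positive direction gives about 3.1–4.5% against a nominal 2.5%, a similar relative increase. These points make the figures illustrative. Step 3 shows that dependence on the unstated model structure could push them up.

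Investigators were kept blind to spray allocation until analysis ended (Study Protocol). For Aim 3 this limits choosing a model because it favours oxytocin. Aims 1 and 2 do not depend on the allocation, and blinding does not hide which model reached significance.

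Finally, the remark about directness compares bias scores with a one-direction response time, whereas a mixed model containing direction can estimate the same push-minus-pull contrast. This weakens directness as an argument for the ANOVA. The better ground is that the plan already presents the ANOVA by default.

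**Conclusion.** The concern holds. The section states a reporting rule that can depend on results, was written with both sets of results known, and covers every aim. Applied on its less favourable reading, it raises the per-aim false-positive rate from about 5% to 6.3–8.4%, or up to 9.0% if the mixed model uses trial-level degrees of freedom. These figures assume two-sided alpha 0.05, by-participant slopes, the noise settings listed, and that every mixed-model p < 0.05 becomes a claim. They are not an upper bound, because the random-effects structure is unstated and an intercept-only model could do much worse.

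The document does not show that any aim switched. The point should be fixed: the inflation under the main assumptions is modest, but a reader cannot judge it from what is written.

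**What to change.** - Delete the conditional reporting rule.
- Let the bias-score ANOVA contrast determine the conclusion for each of the three aims.
- For every aim, report the mixed-model estimate, 95% CI and p-value for the same push-minus-pull contrast as a sensitivity analysis, and state the random-effects structure and the alpha.
- Say plainly that this choice was made after both analyses had been seen. It improves disclosure but does not fully restore error control.
- Qualify the statement that results did not change for any contrast where the two analyses disagree on significance.

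Had one decisive analysis per aim been fixed beforehand, the error would be 0.05 per aim and 1 − 0.95³ = 0.143 over three independent aims without adjustment.

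The cost is wording and one extra table, since both analyses have been run. The downside is that a result significant only in the mixed model can no longer be presented as a main finding.
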